8.3.2. Screening

After the informed consent form has been signed by both the subject and the Principal Investigator or delegate the following information, but not limited to, will be recorded on the case report form (CRF):

Inclusion/Exclusion Criteria Assessment: Refer to criteria above in Sections 7.5.1 and 7.5.2.

Medical and surgical history: Current medical conditions, recent medical history including surgeries and concurrent medications within the last 90 days will be collected. Subjects ASA status will also be assessed.

Demographic information: Such as age, gender, skin pigmentation (see assessment details below), self-identified race/ethnicity etc.

Skin Pigmentation Screening:

Study subjects of differing levels of skin pigmentation will be enrolled in the study.

Subjects will be pre-screened for skin pigmentation (dorsal side of the hand) using the *Delfin SkinColor Catch* device, *Monk* scale,¹ and *Massey-Martin* scale². *Delfin SkinColor Catch* will be the primary stratification method to classify subjects into two groups of light and dark, and *Monk* and *Massey-Martin* scales will be used for data collection purposes.

¹ Massey, DS, Martin, JA. The NIS Skin Color Scale. 2003.

² Monk, E. Monk Skin Tone Scale. 2019. <https://skintone.google/>

Delfin SkinColor Catch provides a colorimetric measure of melanin and erythema and automatically calculates the individual typology angle (ITA, - 90° to 90°) degree, which classifies the skin tone. Delfin SkinColor Catch measurements will be taken on the dorsal side of the hand, following the manufacturer's recommendations provided in Delfin SkinColor Catch User Manual. Notably, three measurements (one measurement between thumb and index finger, upper chest, and forehead) will be taken on a dry, smooth region, free of hair, scars, folds, and hyperpigmentation (i.e., area should be representative of subject's overall skin tone). The following parameters will be recorded: ITA, L, A, B values on the CIE-LAB color space, M and E.

Massey-Martin and Monk are two skin-typing scales, with various shades of skin color corresponding to numeric points 1 to 10. Using a mapped pictorial guide the staff will record the respondent's skin color. Values will be recorded for two sites: dorsal side of the hand and the forehead.

To ensure equal representation of light- and dark- skinned subjects, the collected skin pigmentation data will be reviewed where applicable to ensure recruited subjects represents adequate spread for both light- and dark-skin groups and are not concentrated near the ITA cutoff of 10.

Sensor site screening: Sensor application sites (e.g., wrist) will be screened for tattoos. Tattoos near the sensor site will be documented in the case report form. Subjects that have a tattoo(s) in the area of device placement may be disqualified; per PI and/or study staff discretion.

Physical examination: Including height, weight, calculated Body-Mass Index (BMI), and Allen's test. A directed physical examination with focus on cardiovascular and respiratory systems with airway examination and a focused neurological and musculoskeletal examination will be performed and assessed. Reported outcome as either WNL, NCS, or CS (within normal limits, not clinically significant or clinically significant). Comments added if NCS or CS to explain selection in Case Report Form (CRF).

Vitals: Vital signs, such as blood pressure and heart rate, will be recorded for subject safety monitoring. Pulse oximetry measurements, such as SpO₂, SpCO, and SpHb, may also be recorded.

EKG: A 12-Lead EKG will be completed and reviewed by the Principal Investigator or delegate, if the subject has a clinically significant abnormal EKG the subject will be disqualified.

Pulmonary function test (PFT) assessment: PFT via Spirometry will be completed and reviewed by the Principal Investigator or delegate, if the subject has a clinically significant abnormal PFT the subject will be disqualified.

Venous Blood Samples: Blood samples will be taken (approximately 15 cc). One blood sample will be analyzed via co-oximeter for carboxyhemoglobin (COHb)/methemoglobin (MetHb) levels. The local laboratory will assess the hemoglobin electrophoresis sample to screen out any hemoglobinopathies, which may take up to 72 hours for analysis.

Urine samples: Urine drug screening to test for the presence of drugs such as amphetamines, barbiturates, benzodiazepines, marijuana, and opiates. and cotinine tests. Adult female subjects will be required to take a pregnancy test. Results will be noted. If the pregnancy test is positive, the subject will be removed from the study and notified of their pregnancy test results.

8.4. Data Collection Phase (Visit 2)

8.4.1. Desaturation General

If accepted into the study, standard noninvasive monitors may be placed on the subject, which may include FDA-cleared pulse oximeters, ECG, and blood pressure cuff(s). This is assessed for subject monitoring only. Blood pressure may be obtained from arm cuffs, leg cuffs, finger cuffs, or equivalent devices.

Transient increases in blood pressure and heart rate can be expected during line placement, needle sticks, blood draws, etc. and may also be attributed to anxiety/nervousness relating to a new environment. In the case where heart rate and blood pressure

changes suggest participant discomfort or a potential safety concern, the participant will be removed from the study after qualifying, according to the discretion of medical and study staff.

A peripheral venous line may be placed in the subject's hand or arm for safety purposes. This line may be used for a qualifying blood draw to verify that the participant meets inclusion criteria.

Local anesthetics such as Lidocaine may be used in the event that an IV is placed to numb the site. Subjects will be given the option to have lidocaine be used during IV placement for the purpose of making catheter placement more comfortable.

The subject will be lying-in a supine position and should refrain from excessive movement during the study.

Masimo W1™ and Apple Watch Series 8 will be placed, per the manufacturer's instructions, on the subject's wrist(s) along with at least one FDA-cleared RD SET Adt which may be covered with an ambient light shield. Sensors may be repositioned, as needed, to ensure proper placement. The site of sensor placement should be assessed throughout the duration of the study. If there are any signs of loss of skin integrity and/or loss of circulation or perfusion, the device should be repositioned.

During the study, study devices may be captured using digital photography. These photos will not be used to intentionally capture the subject's identifying features. These digital images may be used to verify proper sensor placement. They may be used in research, product development, product testing, training, and comparison study purposes. In studies with digital photography subjects will give consent for the photography prior to the start of any study-related activities. Consenting to photography does not determine a subject's ability to qualify for the study, subjects may decline photography and still qualify to participate.

Subjects will wear a mask during the desaturation procedure. The mask may be secured to the subject's face by Tegaderm adhesive dressing (or equivalent) to secure the mask to the skin. Subjects may be asked to shave the area of application to allow the mask to adhere to the skin. The area of application may also be wiped to remove facial oils, make-up, or any other skin products.

The gas mixture will include varying proportions of oxygen, carbon dioxide, and nitrogen. The proportion of oxygen in this mixture will be decreased to lower the subject's blood oxygen saturation. The lowest targeted value will be 70% oxygen saturation. Note: At any point in the study, if the subject feels uncomfortable, the subject will be given oxygen.

There may be two types of desaturations, a subject can participate in: Condition A and/or Condition B-1, B-2, B-3 in the same visit.

8.4.1.1. Condition A: Slow Desaturation

The subject may participate in a slow desaturation procedure (Condition A)

In this desaturation (Condition A) the subject will have their palms facing down. The Apple Watch Series 8 will have manual spot checks taken approximately every minute after 1 minute of each desaturation level transition and noted in Masimo data collection software.

See **Figure 4** below for an example of the spot checks distributed approximately 1 minute throughout the slow desaturation procedure.

Figure 4 Example of a Desaturation sequence for Condition A Slow Desaturation

8.4.1.2. Condition B: Fast Desaturation

Figure 5 Example of each Desaturation sequence for Condition B Fast Desaturations

8.4.1.3. Ending Procedure

At the conclusion of the procedure, the sensor(s)/device(s) and IV(s) will be removed. The subject will be allowed to leave after medical personnel determine it is safe to do so.

All subjects will be encouraged to remain in the study area until they feel fit to leave.

Subjects will be given instructions on post care. All subjects will be instructed to contact the principal investigator and/or study staff in the event of any potential complication.

Subjects will be paid according to the compensation breakdown on the consent form.

8.5. Follow-Up Phase (Visit 3)

Each subject will receive a follow-up phone call from the Principal Investigator/delegate within 48-hours after completion of the data collection phase.

9. MONITORING PLAN

As the sponsor of this clinical investigation, Masimo Corporation is required by 21 CFR Part 812, of the Food and Drug Administration regulations to monitor and oversee the progress of the investigation. The monitor(s) assigned by Masimo Corporation to this task will be trained on departmental Standard Operating Procedures (SOPs) on conduct and monitoring of sponsored studies.

In accordance with good clinical practices guidelines, there will be at least three scheduled monitoring visits to ensure overall regulatory compliance of the study:

- An initiation visit, prior to any subject enrollment to confirm site readiness, and to document training on the study protocol and procedures, and use of equipment.
- At least one monitoring visit during initial enrollment, and/or every 2-4 weeks thereafter until completion of the study.

- A final close out visit after the last subject had finished the study.

The monitor will contact and visit the investigator and will be allowed, on request, to have access to all source documents needed to verify the entries in the CRFs and other GCP-related documents (IRB approvals, IRB correspondences, and ICFs), provided that subject confidentiality is maintained in agreement with HIPAA regulations. The Investigator will provide the monitor access to all necessary records to ensure the integrity of the data (21 CFR 812).

It will be the monitor's responsibility to inspect the CRFs at regular intervals throughout the study, to verify the adherence to the CIP and the completeness, consistency, and accuracy of the data being entered on them.

During each visit, the monitor will also verify adherence to the inclusion/exclusion criteria, and documentation of SAEs/SADEs and protocol deviations/violations and check the CRF against source documentation.

After each visit, the monitor will provide a follow-up letter to the Investigator within four weeks of visit completion. The monitoring report will detail findings and open action items observed during the visit. It is the responsibility of the PI and study coordinator(s) to respond to the findings of the monitoring report and complete any open action items as soon as possible but no later than 60 days of receiving the follow-up letter. Any open action items not completed within the time allowed may be sufficient grounds for study site suspension or termination; it will be up to the sponsor to determine whether any incomplete action items are sufficient grounds for suspension or termination.

Depending on the quality of the data and/or changes to factors affecting subject safety, additional monitoring visits may be necessary at the sponsor's discretion.

10. STATISTICAL DESIGN AND ANALYSIS

10.1. Slow Desaturation

10.1.1. Sample Size

10.1.1.1. This study will include at least 10 Dark skin pigmentation subjects based on ISO-80601-2-61.

10.1.1.2. This study will include at least 10 Light skin pigmentation subjects based on ISO-80601-2-61.

10.1.2. Exclusion Criteria

10.1.2.1. Reference device malfunction and/or provides inconsistent SpO₂ value.

10.1.2.2. Data corruption by device failure or data communication problems.

10.1.2.3. Incomplete study or early termination, where the desaturation protocol could not be completed.

10.1.2.4. Discontinuities and abrupt dropouts due to instruments recalibration or device failure.

10.1.2.5. Low signal quality, e.g. due to noise or interference.

10.1.2.6. Subject's oxygen saturation is unstable. This is determined using multiple consecutive SpO₂ values from reference the device, to be stable within 2% SpO₂ (as obtained from a reference device) to include the measurement pair.

10.1.3. Accuracy Calculations

Accuracy will be reported as the Bias, Precision and A_{RMS} using the following equations:

$$Bias = \frac{1}{n} \sum_{i=1}^n (Test\ SpO_2 - Reference\ SpO_2)$$

$$Precision = \sqrt{\frac{\sum_{i=1}^n (Test\ SpO_2 - Reference\ SpO_2) - Bias)^2}{n}}$$

$$A_{RMS} = \sqrt{\frac{\sum_{i=1}^n (Test\ SpO_2 - Reference\ SpO_2)^2}{n}}$$

The precision and A_{RMS} values will be adjusted to account for repeated measurements on each subject.

10.1.4. No Read Rate for Spot Checks:

$$No\ Read\ Rate = (Nf / N_{spotcheck}) \times 100\ (%)$$

Where, Nf = Number of Spot Checks without Valid SpO_2

$N_{spotcheck}$ = Number of All Spot Checks using Apple Watch

No Read Rate will be calculated for overall and for each no-motion and motion spot check subgroup.

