2. OVERALL SYNOPSIS OF THE CLINICAL INVESTIGATION

Clinical investigation title:	Performance Comparison between Masimo W1™ and Apple Watch Series 8
Study objective(s):	
Primary Objective: Evaluate the performance of Masimo W1™ against FDA cleared hospital grade pulse oximetry technology under desaturation conditions.
 
Secondary Objective: Compare the performance of Masimo W1™ and Apple Watch Series 8 against FDA cleared hospital grade pulse oximetry technology under desaturation conditions.

Study device(s):	Masimo W1™ Apple Watch Series 8 Masimo RD SET Adt
Number of subjects:	Up to 40 subjects.
Inclusion criteria:	
 Subject is 18 to 55 years of age. Subject is American Society Anesthesiologist status 1 (ASA I) Subject has a BMI between 18 and 35. Subject is able to read and communicate in English and understands the study and the risks involved.

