Exclusion criteria:	
 Subject is currently taking any medications which in the opinion of the principal investigator would not be suitable for participation in the study. Subject is wearing nail polish that cannot be removed, gel nails, and/or acrylic nails that can interfere with study device's placement. Participants with conditions or skin abnormalities at or around site of sensor placement that could affect the placement on the sensor or prevent monitoring of physiological parameters during the study, such as psoriasis, eczema, angioma, scar tissue, burn, fungal infection, substantial skin breakdown. Subject has participated in an investigational drug study within one month prior to the start of the study. Subject has failed the Allen's Test to confirm patency of the collateral artery. Subject is female with a positive pregnancy test, or is female and is unwilling to use effective birth control between the time of screening and study termination. Subject has a positive urine cotinine or drug test. Subject has a reported allergy to Lidocaine. Subject has clinically significant anemia or other hemoglobinopathy. Subject has a room air saturation of less than 95% by pulse oximetry. Subject has a clinically significant abnormal EKG. Subject has a clinically significant abnormal pulmonary function test via spirometry. Subject is intolerant to a breathing mask apparatus. Subject has a COHb greater than 3%, or MetHb greater than 2% verified by laboratory co-oximeter. Subject has another condition, which in the opinion of the principal investigator would not be suitable for participation in the study. Subject is unwilling or unable to provide informed consent or comply with the study procedures.
Duration of the clinical investigation:	Expected duration of study enrollment is 1 to 3 months. Subject participation in the study will be approximately 6 hours (approx. 2 hours for the screening phase and 4 hours for the data collection phase)

Study endpoint(s):	Primary endpoint: Performance of oxygen saturation (SpO ₂) measurements reported by Masimo W1™. Secondary endpoint: Performance of oxygen saturation (SpO ₂) measurements reported by Masimo W1™ watch and Apple watch series 8.
--------------------	---

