3. IDENTIFICATION AND DESCRIPTION OF THE INVESTIGATIONAL DEVICE

Masimo Corporation is the developer of noninvasive technologies for the measurement and monitoring of physiological variables, such as arterial oxygen saturation (SpO₂), total hemoglobin concentration (SpHb), carboxyhemoglobin concentration (SpCO), methemoglobin concentration (SpMet), and other physiological variables to improve patient outcomes and reduce cost of care.

The Masimo W1™ is a watch that provides spot-check ECG measurements and continuous measurements of functional oxygen saturation of arterial hemoglobin (SpO₂), pulse rate (PR), and respiration rate from the pleth (RRp®). The watch has a touchscreen display, a rechargeable battery, and Bluetooth® connectivity to pair to a smartphone App.

Figure 1: Masimo W1™

Additional study devices that will be used in this study include the Apple Series 8 watch, the Masimo Rad-97 Pulse CO-Oximeter and the Masimo RD SET Adt sensor. The Rad-97 and Masimo RD SET are indicated for the continuous non-invasive monitoring of functional oxygen saturation (SpO₂), pulse rate (PR), respiratory rate (RRa), and Pleth Variability index (PVi) for adult populations.

The Apple Series 8 watch will be connected to an iPhone, results from the spot check measurements on the Apple Watch will also be manually recorded in the comments portion of a data collection software on a laptop. The Rad-97/RD SET pulse oximeter will be connected to a data collection software on a laptop.

Figure 2: Masimo Rad-97 Pulse CO-Oximeter

Figure 3: Masimo RD SET Adt Sensor

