6. OBJECTIVES OF THE CLINICAL INVESTIGATION

Primary Objective: Evaluate the performance of Masimo W1™ against FDA-cleared hospital grade pulse oximetry technology under desaturation conditions.

Secondary Objective: Compare the performance of Masimo W1™ and Apple Watch Series 8 against FDA-cleared hospital grade pulse oximetry technology under desaturation conditions.

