7. DESIGN OF THE CLINICAL INVESTIGATION

7.1. General

Data using the noninvasive devices will be collected from generally healthy male and female volunteers undergoing a desaturation procedure. Study subjects of differing levels of skin pigmentation will be enrolled in the study.

This is a nonrandomized single arm study wherein all subjects are enrolled into the experimental arm and receive Masimo W1™ and Apple Watch Series 8 on their wrist(s) and FDA-cleared RD SET Adt on at least one finger. Desaturation will be conducted by reducing the concentration of oxygen the study subject breathes in a controlled manner to obtain noninvasive oxygen saturation readings, SpO₂, at various levels.

SpO₂ performance will be calculated using Accuracy Root Mean Square (A_{RMS}) analysis of the SpO₂ values and the reference FDA-cleared RD SET Adt values.

Outcome Measure:

SpO₂ equivalence will be determined by calculating the A_{RMS} value through the comparison of the noninvasive oxygen saturation measurement (SpO₂) to the noninvasive oxygen saturation measurement (SpO₂) value obtained from the FDA-cleared hospital grade pulse oximetry technology.

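### For slow desaturation, section 10.1.3 does not say which continuous W1 samples enter A_RMS or whether they match the Apple spot checks, and it plans no between-watch difference or interval

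*Combined protocol and SAP*

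**What the plan says.** The synopsis (section 2) titles the study "Performance Comparison between Masimo W1™ and Apple Watch Series 8", and the secondary objective in section 6 is to "Compare the performance of Masimo W1™ and Apple Watch Series 8 against FDA-cleared hospital grade pulse oximetry technology under desaturation conditions". The secondary endpoint is the performance of SpO2 "measurements reported by Masimo W1™ watch and Apple watch series 8". Section 7.1 states that "performance will be calculated using Accuracy Root Mean Square" analysis against the RD SET values. All subjects wear both watches.

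The watches are read differently. Section 3 says that W1 "provides spot-check ECG measurements and continuous measurements of functional oxygen saturation", whereas Apple spot-check results "will also be manually recorded in the comments portion of a data collection software". In Condition A (section 8.4.1.1) the Apple Watch has "manual spot checks taken approximately every minute after 1 minute of each desaturation level transition". No corresponding schedule is given for W1.

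On analysis, section 10.1.3 states: "Accuracy will be reported as the Bias, Precision and A_{RMS} using the following equations". The formulas sum test minus reference over i = 1 to n. Precision and A_RMS are to be adjusted for repeated measurements, by a method that is not named. Section 10.1.2.6 keeps a measurement pair only when the reference is stable within 2%, and 10.1.2.5 removes low signal quality. Section 10.1.4 defines a no-read rate with Apple spot checks as its denominator.

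**The concern.** A_RMS depends on which moments are sampled. If error grows as saturation falls, a sample set with more low-saturation moments gives a larger A_RMS for the same watch. The W1 value may rest on a continuous record and the Apple value on checks about a minute apart, less those that returned nothing. An Apple no-read has no test value, so it cannot enter Apple's A_RMS; it appears only in a separate Apple-only rate. W1 has no such accounting.

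The plan would then yield two A_RMS values with no paired difference and no interval. A reader could not tell a real difference between the watches from chance, or from a difference in the moments sampled. The choice of W1 samples would also be left to the analyst, and W1 is the sponsor's own device.

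**Working it through.** **1. What the visible text settles.** The slow-desaturation provisions were checked against three questions.
- *Which W1 samples form n?* Section 10.1.3 does not say. Section 10.1.2.6 filters on reference stability; it does not choose among continuous W1 values or set an interval or averaging window.
- *Are they the Apple moments?* Section 8.4.1.1 schedules Apple checks only, and nothing visible ties W1 values to them.
- *Is there a contrast or interval?* None is stated. The repeated-measurements sentence promises adjusted values, not an interval.

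The plan gives no alpha, power, SD, margin or A_RMS limit, so there is no such figure to reproduce. The sample size is consistent: 10 dark + 10 light (10.1.1) = 20, the completion number in 7.3. The 40 in 7.5.3 is an enrolment ceiling and is not used as an analysis size here.

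**2. Effect of different moments (all inputs assumed).** With no bias within a saturation band, A_RMS = sqrt(sum of w_k × s_k²), where w_k is the share of samples in band k and s_k the error SD there. Both watches have the same s_k, and the bands are equal thirds before any loss.
- *Mild case:* s = 1.5, 1.75, 2.0; no-reads 5, 10, 20% (mean 11.7%). All moments: sqrt(9.3125/3) = 1.762. After no-reads: sqrt[(0.95×2.25 + 0.90×3.0625 + 0.80×4)/2.65] = sqrt(3.054) = 1.748. Gap 0.014.
- *Stronger case:* s = 1.5, 2.25, 3.0; no-reads 5, 20, 50% (mean 25%). All moments: sqrt(16.3125/3) = 2.332. After no-reads: sqrt[(0.95×2.25 + 0.80×5.0625 + 0.50×9)/2.25] = sqrt(4.75) = 2.179. Gap 0.152, with Apple looking better.
- *Opposite direction:* s = 1.5, 2, 2.5; W1 samples weighted 50/30/20%, Apple in equal thirds. W1: sqrt(0.5×2.25 + 0.3×4 + 0.2×6.25) = sqrt(3.575) = 1.89. Apple: sqrt(12.5/3) = 2.04. Gap 0.15, with W1 looking better.
- *No effect:* if no-reads are unrelated to error, or W1 loses the same moments, the gap is zero.

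**3. Sampling error of the difference (all inputs assumed).** Each error is a subject offset plus independent within-subject noise. There are 20 subjects, 20 checks per watch, identical watches, and subject offsets correlated between watches. The half-width is 1.96 × the SD of the simulated A_RMS difference (20,000 studies per cell).

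| Between / within SD | True A_RMS | Corr. 0 | Corr. 0.5 | Corr. 0.9 |
|---|---|---|---|---|
| 0.5 / 1.5 | 1.58 | 0.17 | 0.17 | 0.16 |
| 1 / 1.5 | 1.80 | 0.29 | 0.27 | 0.20 |
| 1.5 / 2 | 2.50 | 0.45 | 0.41 | 0.28 |
| 2 / 2 | 2.83 | 0.65 | 0.58 | 0.36 |

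The range is about 0.16 to 0.65 points. Coverage of a leave-one-subject-out jackknife interval with t on 19 df was 0.945 to 0.950 throughout.

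**4. Timing between Apple and the reference.** As a pessimistic case, take both as independent uniform draws over a stable range of width w, which adds variance w²/6. With w = 2, sqrt(A² + w²/6) − A is 0.21 for A = 1.5 and 0.12 for A = 2.83; with w = 1 it is 0.06 and 0.03.

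**The case against.** The strongest reply is that the text promises no contrast. The objective compares the watches against the reference oximeter, the endpoint is the performance each watch reports, section 7.1 defines performance as A_RMS against RD SET, and no hypothesis, margin or superiority claim appears. This stands. A reader might infer that the plan breaks a commitment to a head-to-head test, and the documents do not support that. What remains is that side-by-side values still need common moments and stated uncertainty to be compared, and that the W1 sample set is undefined under either reading.

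Second, the plan has safeguards: the 2% stability filter, the signal-quality exclusion, the one-minute wait after a transition, and a published Apple no-read rate. They reduce the problem. They do not equalise the mix of saturation levels between the watches or put no-reads on a common footing.

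Third, the half-widths in step 3 are ordinary sampling error with 20 subjects, and matching would not remove them. This also stands, and it would be wrong to present them as the size of the sampling-rule gap. If the watches share reference error at matched moments, the half-widths could be smaller than shown.

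Fourth, a rule might exist out of sight: section 8.1 is redacted and Figure 4 is not shown. The point is therefore limited to the visible text.

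**Conclusion.** The point holds as an improvement the sponsor should make. On the visible text, the slow-desaturation A_RMS values for the two watches need not refer to the same moments, and their difference carries no stated uncertainty.

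Two sizes should be kept apart, both on assumed inputs. Different sampled moments can separate equally accurate watches by about 0.01 to 0.15 points, or zero if no-reads are unrelated to error. More extreme assumed weights would give larger gaps, but nothing in the documents supports choosing them. Separately, chance alone gives a 95% half-width of about 0.16 to 0.65 points with 20 subjects.

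Two stronger readings are not supported. One is that the plan favours a particular watch: the direction depends on weights and no-read patterns that the documents do not give. The other is that the fast-desaturation comparison fails in the same way: the Detection Rate in 10.2.3 uses events defined by the reference, so it largely avoids the unequal-moments problem, although it too has no interval.

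**What to change.** In 10.1.3, state which W1 samples form the all-data A_RMS used for the primary objective. For the secondary objective, add the following.
- **Matched set:** all Apple spot-check attempts that pass the reference and data-capture exclusions in 10.1.2, with W1 and reference values taken within a stated time window of the logged check.
- **No-reads:** a missing value from either watch at such an attempt counts as a no-read, not an exclusion. Report both watches' rates over the same attempts.
- **Comparison:** Bias and A_RMS for both watches where both read, and the W1-minus-Apple difference in each, with a 95% CI that treats the subject as the unit (for example a leave-one-subject-out jackknife with t on n − 1 df).
- **Check on selection:** the both-read set describes only moments when Apple succeeded, so also report W1 A_RMS over all attempts at which W1 read.
- **Sensitivity:** repeat with a second window width.

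The cost is SAP wording, a convention for when the Apple comment is entered, alignment of W1 times to the logged checks, and fewer W1 pairs in the comparison. No subjects or procedures are added. Timing mismatch between Apple and the reference already exists under the current plan and is not a cost of this change; the second window shows its effect. The only effect on the primary analysis is that its W1 sample set becomes specified.
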